6.3.2 Blinding and Code-breaking Procedures

The study will be performed in a modified double-blind (observer-blind) fashion:

- Investigators and study staff who conduct the safety assessment and the participant will not know which vaccine is administered in order to decrease the risk of potential bias
- Only the study site staff who prepare and administer the vaccine and are not involved with the safety and efficacy evaluation will know which vaccine is administered
- Testing laboratories will be blinded

The code may be broken in the event of an AE only when the identification of the vaccine received could influence the treatment of the participant. Code-breaking should be limited to the participant(s) experiencing the AE.

The blind of individual participants can be broken by the Investigator or a delegate through the IRT system, as explained in the code-breaking procedures described in the Operating Guidelines. Once the emergency has been addressed by the site, the Investigator or a delegate must notify the Sanofi Pasteur RMO if a participant's code was broken. All contact attempts with the Sponsor prior to unblinding are to be documented in the source documents, and the code-breaking CRF is to be completed.

The Institutional Review Board/Independent Ethics Committee (IRB / IEC) must be notified of the code-breaking, in accordance with local regulations. All documentation pertaining to the event must be retained in the site's study records and in Sanofi Pasteur's files. Any intentional or unintentional code-breaking must be reported, documented, and explained, and the name of the person who requested it must be provided to the Sponsor.

A request for the code to be broken may also be made by the Global Pharmacovigilance (GPV) Department through an internal system for reporting to Health Authorities in the case of an SAE, as described in International Council for Harmonisation (ICH) E2A^a. In this case, the code will be broken only for the participant(s) in question. The information resulting from code-breaking (ie, the participant's vaccine or group assignment) will not be communicated to either the Investigator or the immediate team working on the study, except for the GPV representative.

The code-breaking procedures are described in the Operating Guidelines.

^a All unexpected and related SAEs submitted to European Union competent authorities must be unblinded.

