The blind will be broken by the Sponsor at the time of the ESDR (with access to study intervention assignments [for the Sentinel Safety Cohort participants only] to a limited number of Sponsor Study Staff members comprising the Core Safety Management Team) and at the time of the first interim analysis after the first database lock. However, participant-level data will be maintained blinded on site until the end of the study/until the interim Clinical Study Report approval.

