8.4 Adverse Events and Serious Adverse Events

Safety will be described in all study participants.

The definitions of an AE, SAE, and the different categories of AEs can be found in [Appendix 10.3](#).

AEs will be reported by the participants to the investigator, then by the Investigator to the Sponsor.

The Investigator and any qualified designees are responsible for detecting, documenting, and recording events that meet the definition of an AE or SAE and remain responsible for following up AEs that are serious, considered related to the study intervention or study procedures, or that caused the participant to discontinue the study (see [Section 7](#)).

An ESDR will be performed for Sentinel Safety Cohort participants. The goal of ESDR is to allow the preliminary safety assessment for a cautious, step-wise approach to vaccine administration, starting with participants aged 18-49 years, as there is no previous human data for the CoV2 preS dTM candidate vaccine.

Sentinel Safety Cohort

The participants' enrollment will include the following sequential steps:

- Step 1:
 - Thirty participants aged 18-49 years from Cohort 1 will be enrolled in the Sentinel Safety Cohort, whereafter enrollment will be paused.
 - Six participants will be randomly assigned to each of the 5 dosing groups defined in Cohort 1: 5 µg and 15 µg AF03-adjuvanted groups, 5 µg and 15 µg AS03-adjuvanted groups, and placebo.
 - Early safety data collection is planned 8 days after the completion of the vaccination (D09, including safety laboratory data); and ESDR is to be planned as soon as possible. Limited members of the Sponsor Study Team (RMO, Biostatistician and Programmer, Pharmacovigilance Science Expert, and Global Safety Officer) will review unblinded safety data and will provide their recommendation to continue the recruitment.
- Step 2: If there is no safety signal after the ESDR after the completion of the vaccination in Sentinel Safety Cohort, recruitment will reopen to all dosing groups and both age strata.

ESDR

The safety data collected for ESDR for Sentinel Safety Cohort will be reviewed by the Investigator. The intensity of non-serious AEs/adverse reactions (ARs) will be assessed using the Sanofi Pasteur scale.

The following safety parameters will be assessed as part of the early safety data review for the Sentinel Safety Cohort participants after the first injection of CoV2 preS dTM candidate vaccine:

- Immediate reactions

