- Solicited injection site and systemic reactions
- Laboratory abnormalities (including hematology, chemistry, coagulation time, and urinalysis)
- Unsolicited AEs reported as vaccine related by the Investigator
- SAEs and AESIs

If any of the below criteria are met, the data on the particular alert threshold event will be reviewed by the SMT and a decision will be made as to whether subsequent vaccinations in the study will be allowed to resume. Enrollment will be paused during the ESDR, and the following safety parameters will be examined:

- ≥ 2 participants per dosing group (n=6) experiencing Grade 3 systemic reaction (without concurrent infectious disease)
- ≥ 2 participants per dosing group (n=6) experiencing Grade 3 solicited injection site pain
- ≥ 2 participants per dosing group (n=6) experiencing Grade 3 unsolicited non serious reactions (reactions not explained by any other possible etiology)
- ≥ 2 participants with Grade 3 laboratory AE (Grade 3 abnormality if Grade 1 or 2 at baseline) of the same type (reactions not explained by any other possible etiology)

- ≥ 2 participants with Grade 2 laboratory AE (Grade 2 abnormality if normal at baseline) of the same type (reactions not explained by any other possible etiology) and judged by the Investigator to be clinically meaningful
- Any related SAEs

Following the ESDR and resumption of enrollment and dosing, occurrence of any one of these criteria will result in a pause in enrollment and vaccination pending Sponsor decision. The study status and final Sponsor decision will be submitted for notification to the IRB/IEC.

Halting Rules throughout the Study

Blinded safety data will be reviewed by limited members of the Sponsor Study Team (RMO, Biostatistician and Programmer, Pharmacovigilance Science Expert, and Global Safety Officer) at regular intervals to identify any new safety signals or safety concerns during the conduct of the study. A pause might be recommended in both recruitment and/or further vaccination while it investigates any potential signal or concern.

Enrollment will be paused during the review and the data will be examined if:

- Any of the following events, assessed as related to the vaccine by the Investigator and the Sponsor, are reported in the study:
 - SAE
 - New Onset of Potential immune-mediated diseases (pIMDs)
 - Ulceration, abscess or necrosis at the injection site

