 - Four or more participants across treatment groups experience the same Grade 3 AE of the same type in the absence of any other etiology
 - Two or more participants across treatment groups experience the same Grade 3 laboratory abnormality assessed by the investigator as clinically significant
- Any of the following events, suggestive of vaccine associated enhanced disease, are detected in the study including:
 - Any death due to SARS-CoV-2 infection
 - $> 10\%$ of the study population is hospitalized due to SARS-CoV-2 infection
 - ≥ 4 ICU admissions among participants ≥ 50 years due to SARS-CoV-2 infection
 - ≥ 8 ICU admissions among participants 18-49 years due to SARS-CoV-2 infection

Case unblinding may be performed if necessary.

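### After the early safety review, the mandatory vaccination pause for Grade 3 clinical reactions rests on a per-group count that the plan gives to nobody; the study-wide rule of four, which can be counted blind, requires only an enrollment pause

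*Protocol*

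**What the plan says.** Protocol Section 8.4 has two lists that both apply once dosing resumes after the ESDR.

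- **ESDR criteria, carried forward.** There are six. Three count Grade 3 clinical reactions (systemic reactions, injection site pain, unsolicited non-serious reactions) at two or more per group. The first concerns "participants per dosing group (n=6) experiencing Grade 3 systemic reaction (without concurrent infectious disease". All three keep the n=6 of the sentinel stage, where the groups were "the 5 dosing groups defined in Cohort 1". The other three need no group count: two same-type Grade 3 laboratory AEs, two same-type Grade 2 laboratory AEs judged clinically meaningful, and any related SAE. After the ESDR, "occurrence of any one of these criteria will result in a pause in enrollment and vaccination pending Sponsor decision".
- **Halting rules throughout the study.** The obligatory action is different: "Enrollment will be paused during the review and the data will be examined if" a listed rule is met. One rule, for events assessed as related by Investigator and Sponsor, is "Four or more participants across treatment groups experience the same Grade 3 AE of the same type in the absence of any other etiology". Others cover related immune-mediated disease, injection-site necrosis and COVID-19 death. On vaccination the text is permissive: "A pause might be recommended in both recruitment and/or further vaccination while it investigates any potential signal or concern".

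The review under the halting rules uses blinded data. Section 6.3.2 opens assignments to the Sponsor at the ESDR for sentinel participants only, "and at the time of the first interim analysis after the first database lock". Section 9.5 bases that interim on safety data to D43, which is after the second injection at D22. At the sites, only staff "who prepare and administer the vaccine and are not involved with the safety and efficacy evaluation will know which vaccine is administered". An Investigator may break the code for an AE only where knowing the vaccine could change treatment, and pharmacovigilance may request it for an SAE. Section 8.4 also permits case unblinding where needed, without saying when. There is no data monitoring committee (Section 9.6).

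**The concern.** The two lists attach different obligations to the same kind of event, and the stricter one turns on information that the plan does not provide. Whoever watches Grade 3 reactions after the ESDR can see a pooled count. They cannot see whether two of the cases fall in one dosing group, which is what decides whether vaccination must stop.

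Followed as written, a mandatory stop could be met without anyone knowing it. Participants in Cohort 2 would go on receiving a second dose of a new antigen, in most arms with an adjuvant, unless someone uses discretion. Section 10.8 gives consistency with the overall halting rules as the reason for one ESDR threshold, so the two lists seem meant to work together.

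**Working it through.** **1. Injections at stake.** From Table 4.2:

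- Younger adults: Cohort 1 is 5 × 20 = 100; Cohort 2 is 20 + 60 + 20 + 60 + 20 + 20 = 200; total 300.
- Older adults: Cohort 1 is 5 × 10 = 50; Cohort 2 is 10 + 30 + 10 + 30 + 10 = 90; total 140.
- The sum is 440, as stated. Cohort 2 is 200 + 90 = 290.

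The first injection is given at the randomization visit (Tables 1.1 and 1.2), so an enrollment pause already stops first injections. The two obligations differ only for the 290 second injections.

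**2. The lists side by side.**

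| Event after the ESDR | Carried-forward criteria (enrollment and vaccination) | Study-wide rules (enrollment only) |
|---|---|---|
| Related SAE | 1, any group | 1 |
| Grade 3 laboratory, same type | 2, any group | 2 |
| Grade 2 laboratory, same type, clinically meaningful | 2, any group | none |
| Grade 3 systemic, pain or unsolicited | 2 in one dosing group | 4 across groups, same type |
| Grade 3 erythema or swelling | none | 4 across groups, same type |
| Related immune-mediated disease, site necrosis, COVID-19 outcomes | none specific | listed |

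In the first three rows the stricter action can be taken on blinded data. In the fourth row it cannot. In the last two rows nothing specific to the event obliges a vaccination pause.

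**3. How often the fourth event hides a mandatory stop.** I read dosing group as Groups 1 to 11 with ages pooled: eight groups of 30, two of 90 and one of 20 (240 + 180 + 20 = 440). Assume each participant is equally likely to have the event. After k events among N participants,

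P(some group holds at least 2) = 1 − e_k / C(N, k),

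where e_k is the sum, over all sets of k different groups, of the product of their sizes. At k = 4:

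| Events arise among | Group sizes | e_4 | C(N, 4) | P |
|---|---|---|---|---|
| All 440 | 8 × 30, 2 × 90, 20 | 692,820,000 | 1,540,499,290 | 0.550 |
| 380 vaccinees | 6 × 30, 2 × 90, 20 | 307,260,000 | 855,154,755 | 0.641 |
| Cohort 2, 290 | 3 × 30, 2 × 90, 20 | 51,570,000 | 288,641,640 | 0.821 |
| 240 AS03 recipients | 2 × 30, 2 × 90 | 7,290,000 | 134,810,340 | 0.946 |

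**4. Before the fourth event.** The same formula at k = 2 and 3 gives 0.121 and 0.325 for all 440, and 0.227 and 0.557 within Cohort 2. Here no study-wide rule of four is met, yet a mandatory vaccination pause may be. Injection schedule is not blinded (Section 4.1), so reviewers can restrict to Cohort 2, but that does not settle the question: its six groups can hold one case each, and sharing is certain only at the seventh.

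**5. Where the figures apply.** They cover reactions that count under both lists and are assessed as related. They do not cover erythema or swelling. The systemic criterion counts Grade 3 reactions of any type, so a same-type figure is a floor for it.

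**The case against.** The strongest reply is that the plan already handles this. The same section lets reviewers recommend a pause in vaccination and unblind cases. Contraindications DCI03 and DCI04 (Section 7.1.2) can stop an affected participant, and an internal safety committee monitors throughout. The two lists do not contradict each other either: both apply and the stricter governs. This stands as mitigation. It does not supply the missing count, because no pooled number obliges anyone to unblind.

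It can also be said that no sentence assigns the carried-forward criteria to blinded reviewers. The blinded-review sentence belongs to the halting rules, and the ESDR text names the safety management team. That is correct, and the point is one of silence rather than a stated conflict. But Section 6.3.2 limits the Core Safety Management Team's access to sentinel assignments, all of them in Cohort 1, so that team is not given the count for anyone awaiting a second injection.

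Four stronger readings are tempting and not supported:

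- That every mandatory vaccination pause needs a group count. Three of the six criteria do not.
- That the probabilities hold for any Grade 3 event. Erythema and swelling fall under no per-group criterion, and the rule of four requires relatedness.
- That the gap costs per-protocol participants. Late second doses follow from any vaccination pause; a missed pause would cause fewer.
- That a threshold of two is miscalibrated in groups of up to 90. The documents give no expected Grade 3 rate from which to judge.

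**Conclusion.** The point holds for Grade 3 systemic reactions, injection site pain and unsolicited reactions after the ESDR. Their mandatory vaccination pause depends on group membership, and no passage provides for anyone to have it before the first interim. The rule of four and the other study-wide rules can be counted blind but oblige only an enrollment pause, which leaves the 290 second injections to discretion.

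The size is illustrative: 0.55 to 0.95 at the fourth related same-type event, depending on where events arise, assuming equal risk, full enrollment and pooled ages within Groups 1 to 11.

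This is a minor matter and a cheap improvement. All analyses are descriptive, and discretion exists. Section 9.5 reports a partial database lock by Amendment 1, so dosing was probably complete by this version; the wording would have been needed before dosing resumed after the ESDR.

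**What to change.** In Section 8.4:

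- **(a)** State that meeting any study-wide halting rule pauses both enrollment and vaccination until the Sponsor decides. This needs no unblinding.
- **(b)** For the three per-group clinical criteria after the ESDR, remove the n=6 and define dosing group as Groups 1 to 11 of Table 4.2. Name one unblinded role, for example the pharmacovigilance representative, to check group membership when a second qualifying event occurs within the same cohort, and at later ones until the criterion is met. That role reports only whether the criterion is met. Add a matching exception in Section 6.3.2.

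**Cost of (a).** It adds a vaccination pause where no group holds two at the fourth event: 0.45, 0.36, 0.18 or 0.05 in the four rows above (1 − P). A long pause can push second injections past the +7-day window and so out of the per-protocol set. If due dates spread evenly over E days and a pause lasts L days, about 290 × (L − 7)/E are affected. With E assumed to be 28, that is none at 7 days, 31 at 10 and about 72 at 14. At 14 days it is 97 for E = 21 and 48 for E = 42. SAP Section 5.2.5 already confirms immunogenicity on the full analysis set.

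**Cost of (b).** A few participants are unblinded to one role. Under equal risk the mean number of events up to the first shared group (the sum of e_k / C(N, k) over k ≥ 0) is 4.5 for all 440, 4.1 for vaccinees and 3.0 for AS03 recipients. It can never exceed 12, because there are 11 groups. An event alone in its cohort stays blinded, so fewer are unblinded on average. This is per criterion and up to the first pause; three criteria, and events after resumption, add to it.

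A deadline for the Sponsor decision and a supplementary per-protocol analysis are separate matters that this point does not need.

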8.4.1 Time Period and Frequency for Collecting AE and SAE Information

Immediate Post-vaccination Observation Period

Participants will be kept under observation for 30 minutes after each vaccination to ensure their safety. The post-vaccination observation should be documented in the source document.

Reactogenicity

Solicited injection site reactions will be collected from D01 to D08 after each vaccination.

Solicited systemic reactions will be collected from D01 to D08 after each vaccination.

The solicited injection site reactions and systemic reactions that are pre-listed in the diary cards and CRF, together with the intensity scales, are presented in [Appendix 10.3.5.1.1](#).

Unsolicited Adverse Events

Unsolicited AEs include unsolicited non-serious AEs and SAEs. The intensity grading scale for unsolicited non-serious AEs is presented in [Appendix 10.3.5.1.2](#).

Unsolicited non-serious AEs will be collected from D01 to D22 after each vaccination.

SAEs will be collected and assessed throughout the study, from inclusion until 12 months after the last vaccination (up to D366 for Cohort 1 and up to D387 for Cohort 2). However, before the first study intervention administration, only SAEs related to study procedures are to be collected (eg, SAEs related to blood sampling).

Medical occurrences that begin before the start of study intervention but after obtaining informed consent will not be recorded on the AE section of the CRF.

All SAEs will be recorded and reported to the Sponsor or designee immediately and under no circumstance should this exceed 24 hours, as indicated in [Appendix 10.3](#). The Investigator will submit any updated SAE data to the Sponsor within 24 hours of it being available.

Investigators are not obligated to actively seek AE or SAE after conclusion of the study participation. However, if the Investigator learns of any SAE, including a death, at any time after a participant has been discharged from the study, and he/she considers the event to be reasonably related to the study intervention or study participation, the Investigator must promptly notify the Sponsor.

Medically Attended Adverse Events (MAAEs)

MAAEs will be collected at any time during the study.

Adverse Events of Special Interest (AESIs)

AESIs will be collected at any time during the study.

See [Section 8.4.6](#) for the list of AESIs.

8.4.2 Method of Detecting AEs and SAEs

Individual diary cards, specifically designed for this study by the Sponsor and provided to the study sites, will be given to study participants for the recording of daily safety information. These diary cards will include pre-listed terms and intensity scales as well as areas for free text to capture additional safety information or other relevant details. Participants will also be provided with rulers for measuring the size of injection site reactions, and with standard digital thermometers for measuring daily temperatures. To ensure consistency of reporting, the study sites will instruct participants on how to correctly use these tools.

At specified intervals, the Investigator or an authorized designee will interview the participants to collect the information recorded in the diary card and will attempt to clarify anything that is incomplete or unclear. All clinical study information gathered by the study site will be reported electronically by the Investigator or authorized designee using a web-based CRF. Any information that was not documented in the diary card will first be captured in the source document and then reported electronically.

The 12-month (post-last injection) follow-up will be done by interviewing participants either during a visit or over the telephone using a questionnaire to capture SAEs and AESIs, if applicable.

The method of recording, evaluating, and assessing causal relationship of AE and SAE and the procedures for completing and transmitting SAE reports are provided in [Appendix 10.3](#).

Care will be taken not to introduce bias when detecting AEs and/or SAEs. Open-ended and non-leading verbal questioning of the participant is the preferred method to inquire about AE occurrences.

8.4.3 Follow-up of AEs and SAEs

Unless a participant refuses further contact, each participant who experiences an AE (whether serious or non-serious) during the study must be followed until the condition resolves, becomes stable, or becomes chronic (even after the end of the participant's participation in the study) if *either* of the following is true:

- The AE is considered by the Investigator to be related to the study intervention administered
- The AE caused the discontinuation of the participant from the study or from vaccination

The Investigator will inform the Sponsor of the date of final disappearance of the event or the date of "chronicity" establishment.

8.4.4 Regulatory Reporting Requirements for SAEs

- Prompt notification by the Investigator to the Sponsor of a SAE is essential so that legal obligations and ethical responsibilities towards the safety of participants and the safety of a study intervention under clinical investigation are met.
- The Sponsor has a legal responsibility to notify both the local regulatory authority and other regulatory agencies about the safety of a study intervention under clinical investigation. The Sponsor will comply with country-specific regulatory requirements relating to safety reporting to the regulatory authority, IRB / IEC, and investigators.
- For all studies except those investigating medical devices investigator safety reports must be prepared for suspected unexpected serious adverse reactions (SUSAR) according to local regulatory requirements and Sponsor policy and forwarded to investigators as necessary.
- An investigator who receives an investigator safety report describing a SAE or other specific safety information (eg, summary or listing of SAEs) from the Sponsor will review and then file it and will notify the IRB/IEC, if appropriate according to local requirements.

